APPENDIX 8 PD HALLUCINATION QUESTIONNAIRE

Many patients with Parkinson's disease suffer from what we call hallucinations or apparitions.

We would like to ask you some questions regarding hallucinations.

- a. Do you sometimes feel someone is present who isn't actually there?
- b. Do you sometimes think someone went by who didn't? If so, any one in particular?
- c. Do you see things not seen by others? If so, how many months or years have you been seeing things? what do you see? People? Animals? Relatives? Children? When do you see them? Daytime? Evening? At night? Are they bothersome? Do they upset you? How often does this occur, many times a day? every day? Twice a week? Once a month? Can you provide a narrative description of them below?
- d. Do you mistake objects for animals, like a white cloth for a white cat?
- e. Do you feel like someone is going to harm you or is out to get you?
- f. Do you feel things such as insects crawling up your legs on your hands or strange sensations such as scratching or burning or tingling on your hands?
- g. Do you hear voices that aren't actually there? Do the voices talk to you? To each other? Talk about you?
- h. Do you smell any abnormal smells not smelled by others? Are they unpleasant smells?

Please describe your experience in detail (i.e. what do you hear, see, smell or feel? Make sure you note how many times a day or night or week any of these episodes occur)

- i. Have you been diagnosed with any eye disease? How good is your eyesight? If it's poor, how bad is it? How long have you had poor eyesight? How fast has it been getting worse?
- ii. Do you experience hallucinations while "on" or "off"?
- iii. Has your dopamine dose been changed recently?

iv.

V.

Interviewer's Signature: _____ Date: _____ / _____ / _____

Title:

CONFIDENTIAL

19April21_7.0

PI Review of Interview

Once completed by or reviewed by the PI, please enter any observations or notes of significance regarding this patient.

PI Signature: _____ Date: _____ / _____ / _____

DD MMM YYYY

RASMET	Evaluation of Safety and Tolerability of ENT-01 for the Treatment of Parkinson's Disease Related Constipation
SAE	Serious Adverse Event
SAP	Statistical Analysis Plan
SAPS-PD	The Scale for the Assessment of Positive Symptoms -Parkinson's Disease
SBM	Spontaneous Bowel Movement
SD	Standard Deviation
SOC	System Organ Class
TEAEs	Treatment Emergent Adverse Events
ULN	Upper limit of normal
UPDRS	Unified Parkinson's Disease Rating Scale
US	United States
WHO	World Health Organization

Abbreviation	Definition of Terms
WHO-DD	World Health Organization Drug Dictionary

1. INTRODUCTION AND OBJECTIVES OF ANALYSIS

1.1. Introduction

Constipation is a common problem worldwide, affecting 2% to 27% of the population, with most estimates varying from 12% to 20% (Bouras and Tangalos, 2009). The prevalence of constipation increases to 30%-40% among people aged >65 years and women are disproportionately affected. Constipation is much more common among patients with Parkinson's Disease (PD) than in the general population. There are 1 million people suffering from Parkinson's Disease in the US, of which roughly 60%, or 600,000 suffer from chronic constipation and in most, the condition is chronic, severe and unresponsive to standard therapy (Ondo et al., 2012; Zangaglia et al., 2007). Constipation not only constitutes a major economic burden, but it also significantly affects the quality of life of the individual with Parkinson's disease. An effective prokinetic medication for individuals with PD would be a useful addition to the currently available treatments for this disabling condition.

The individual with Parkinson's Disease suffers from a form of constipation that is believed to be caused principally by delayed transit through the colon. In addition, defecation is often impaired by dysfunction of the Parkinson's Disease subject's anorectal reflex.

The pathophysiology of the gastrointestinal (GI) dysfunction in Parkinson's Disease involves deposition of alpha-synuclein within both the enteric nervous system (ENS) as well as within the brainstem. For reasons that remain unknown alpha-synuclein, which is a protein normally produced in neurons, forms neurotoxic intracellular aggregates in Parkinson's Disease. Squalamine is a small molecule, originally discovered in the liver of the dogfish shark, where it is delivered following a meal via the biliary tract into the intestine (Moore et al., 1993). In a recent study, squalamine has been shown to prevent the formation of toxic alpha-synuclein aggregates (Perni et al., 2017). Squalamine both excites the neurons of the ENS and protects them from alpha-synuclein induced cytotoxicity. We will evaluate squalamine as a therapeutic to treat the constipation associated with Parkinson's Disease and we will explore its effect on sleep architecture and hallucinations/delusions.

A Phase 2a study, *Evaluation of Safety and Tolerability of ENT-01 for the Treatment of Parkinson's Disease Related Constipation (RASMET)* was conducted. The purpose of the study was to assess the safety, tolerability, pharmacokinetics, and pharmacodynamics of an orally administered medication to relieve symptoms of constipation associated with Parkinson's Disease. The results of the study indicated that orally administered ENT-01 was safe and significantly improved bowel function and neurologic symptoms. Minimal systemic absorption suggests that improvements result from local stimulation of the ENS. Data from this study informed the development of the 2b study.

1.2. Objectives of Statistical Analysis

This statistical analysis plan (SAP) is designed to outline the methods to be used in the analysis of study data in order to answer the study objectives. Populations for analysis, data handling rules, statistical methods, and formats for data presentation are provided. The statistical analyses and summary tabulations described in this SAP will provide the basis for the results sections of the clinical study report (CSR) for this trial.

1.2.1 Primary Objective

The primary objective is to evaluate the safety, tolerability, and efficacy of repeated oral doses of ENT-01 for up to 25 days in subjects with Parkinson's Disease related constipation in a randomized, double-blind, placebo-controlled study.

- **Primary Safety Objective:** The primary safety objective of this study will be evaluation of the safety of repeated daily oral doses of ENT-01 for up to 25 days in patients with PD- related constipation.
- **Primary Tolerability Objective:** The primary tolerability objective will be evaluation of recurrent vomiting, recurrent diarrhea, abdominal pain and dizziness.
- **Primary Efficacy Objective:** The primary efficacy objective will be evaluation of the efficacy of repeated daily oral doses of ENT-01 for up to 25 days in improving CSBM rate.

1.2.2 Secondary Objectives

The secondary objectives include:

- To determine if the correct starting dose (75mg or 150mg) can be predicted from the baseline weekly CSBM rate.
- To collect information on the effect of ENT-01 on CSBM, SBM, ease of passage, consistency, suppository/enema use and subjective bowel function and quality of life (QOL).

1.2.3 Exploratory Objectives

The exploratory objectives include:

- To determine the decrease in efficacy in the blinded placebo withdrawal and washout periods.
- To collect information on the effect of ENT-01 on motor and non-motor symptoms of Parkinson's disease including mood, memory, sleep, and hallucinations/delusions.
- To collect information on the effect of ENT-01 on levodopa absorption.
- To collect information on the effect of ENT-01 on the stool microbiome.

2. STUDY DESIGN

2.1. Synopsis of Study Design

This study will be conducted as a multicenter, randomized, double-blind, placebo-controlled study in patients with Parkinson's Disease and constipation.

This study has two parts. The first part of this randomized approximately 72 subjects in a 3:1 to treatment or placebo ratio (double-blind), with approximately 54 subjects allocated to the treatment groups and approximately 18 to placebo. In the second part of the study, an additional 80 patients (approximately) will be randomized 1:1 to treatment or placebo (double-blind) with approximately 40 subjects allocated to each group.

In both parts of the study, the study was conducted as a multicenter, randomized, double-blind, placebo-controlled study. A subject's total study duration was no more than 10 weeks and total active dosing days was a maximum of 25 days.

During the active dosing period, patients will be able to increase/adjust their dose every three days. This is called the Dose Adjustment period. After the subject documents two complete spontaneous bowel movements in three days, the subject will fix at the dose for the remainder of the study. This is called the Fixed Dose period. After completing up to 25 days of dosing, all subjects will be given placebo for 2 weeks (single-blind) followed by 4 weeks of wash-out.

Figure 1. Visit Schedule Overview					
Visit 1	Visit 2	Visit 3	Visit 4	Visit 5	Visit 6
Screening	Randomization and Drug Dispensation	Follow up	Single Blind Placebo Withdrawal	Wash Out	End of Study
Day -14	Day 1	Day 11 +/- 1 day	Day 25 - 3 days	Day 39 +/- 2 days	Day 69 +/- 3 days

2.2. Randomization Methodology

Randomization occurs after all screening assessments have been completed and after the Investigator has verified that they are eligible. In the first part of the study, patients will be

randomized 3:1 to receive either ENT-01 or placebo; in the second part of the study patients are randomized 1:1 to receive either ENT-01 or placebo. Any patient identification numbers that are assigned will not be reused, even if the patient does not receive treatment. The patient's identification (ID) number will be used on that patient's eCRFs and serious adverse event (SAE) forms.

Randomization will be conducted centrally via an Interactive voice/web-response system (IXRS). The randomization will be stratified by the baseline weekly CSBM rate. Subjects with a baseline CSBM rate of 0-0.9 will begin treatment with 150 mg of ENT-01 or 6 tablets of placebo and Subjects with a baseline CSBM rate of 1.0-2.9 will begin with 75 mg of ENT-01 or 3 tablets of placebo. Note that in the second part of the study, the baseline CSBM criteria of 1.0 – 2.9 was modified to 1.0 – 3.0 (i.e., including subjects with a baseline CSBM rate of 3.0).

Instructions for patient screening, registration, number assignment, and enrollment are referenced in the Interactive Response Technology (IRT) vendor manual.

2.3. Stopping Rules and Unblinding

This study may be terminated at the discretion of the Enterin, Inc. or of any regulatory agency for reasons including safety and/or efficacy.

It is anticipated that no more than 2 subjects out of 60 (3.3%) will have an AE of grade 4 or 5 that is at least possibly related to ENT-01 in this Study. Should there be more than 2 subjects with an AE grade 4 or 5 that is at least possibly related to ENT-01 in the cohort of subjects randomized to ENT-01, the study will be put on an immediate clinical hold.

In addition, individual safety stopping criteria will include:

- Reaching DLT before a prokinetic effect
- Having a non-DLT gastrointestinal adverse event > grade 3 within 24 hours of taking ENT-01 that is at least possibly attributable to ENT-01
- A fall in systolic blood pressure to < 80 mm Hg upon rising from lying to sitting or standing
- A fall in diastolic blood pressure to < 40 mm Hg upon rising from lying to sitting or standing
- Elevation of liver function tests (LFTs) > 3 times the upper limit of normal (ULN)

A treatment assignment should only be unblinded in a situation of urgent medical necessity, when the identity of the study medication must be known in order to select continuing therapy for the disease under study or an AE. The decision should be made only after consultation with the unblinded Medical Monitor, unless the urgency of a case requires immediate action.

Treatment assignments can be obtained through a controlled transaction with IXRS. If a treatment code is unblinded for any reason, the Investigator will notify Sponsor within 24 hours and will document the following in the eCRF: who unblinded the code, the reason for doing so, and the date of unblinding.

2.4. Study Procedures

The schedule of events, as outlined in the study protocol, is provided in Table 1.

Table 1. Schedule of Events

	Visit 1 Screening	Visit 2 Randomization	Visit 3 Follow-Up	Visit 4 End of Treatment	Visit 5 End of Placebo	Visit 6 End of Study	Early Termination
	Day -14	Day 1 (+/- 2days)	Day 11 (+/- 1day)	Day 26 (- 2 days)	Day 39 (+/- 2days)	Day 69 (+/- 3 days)	
Informed Consent	X						
Inclusion/Exclusion Criteria ^a	X	X					
Demographics/Medical History	X						
Complete Physical Exam	X						X
Brief Physical Exam			X	X	X	X	
Height	X						
Weight	X	X	X	X	X	X	X
Orthostatic Vital Signs ^b	X	X	X	X	X	X	X
12-lead ECG	X	X	X	X	X	X	X
Labs and Urinalysis	X		X	X	X	X	X
Pregnancy Testing ^c	X	X	X	X	X	X	X
In-clinic IP/Placebo Dosing ^d			X	X	X		
In-clinic Levodopa Dosing		X	X	X	X	X	X
Levodopa PK Draws ^e		X	X	X	X	X	X
IP/Placebo Dispense		X	X	X			
IP/Placebo Collection and Accountability			X	X	X	X	X

	Visit 1 Screening	Visit 2 Randomization	Visit 3 Follow-Up	Visit 4 End of Treatment	Visit 5 End of Placebo	Visit 6 End of Study	Early Termination
	Day -14	Day 1 (+/- 2 days)	Day 11 (+/- 1 day)	Day 26 (- 2 days)	Day 39 (+/- 2 days)	Day 69 (+/- 3 days)	
Instructions to Discontinue Laxatives and other BM Medications	X						
Dispense Rescue Medications ^f	X	X	X	X	X		
Stool Diary Instruction/Review ^g	X	X	X	X	X	X	X
AE Review	X	X	X	X	X	X	X
Prior and Con Meds	X	X	X	X	X	X	X
Rome IV questionnaire	X						
MDS-UPDRS ^h	X		X	X	X	X	X
C-SSRS	X	X	X	X	X	X	X
BDI-II	X		X	X	X	X	X
MMSE	X		X	X	X	X	X
SAPS-PD, Hallucination/Delusion Questionnaire ⁱ	X	X	X	X	X	X	X
PAC-QOL and PAC-SYM		X	X	X	X	X	X
Dispense Stool Collection Kits	X		X				
Collect Stool Sample ^j		X		X			

a. Confirmation of eligibility: To be randomized to receive double-blind study medication in this study, subjects must meet the following criteria:

- Have had at least 11 “Available Data Days” (days with electronic diary compliance sufficient for determining whether a BM occurred)
- Have had <3 CSBMs/week based upon the average CSBM rate during the first 2 screening weeks (baseline period).
- Be approved for randomization by the enrollment committee

b. Three sets will be taken. Time points to be defined. Orthostatic vital signs will include supine BP and HR, sitting or standing BP and HR, RR, and body temperature. Supine measurements will be taken after the subject has been in the supine position for at least 5 minutes. Sitting or standing measurements will be taken within 5 minutes of sitting or standing from the supine position. Respiration rate and body temperature will be taken after the subject has been sitting or standing for at least 5 minutes.

c. For women of child-bearing potential, on-site with urine pregnancy test kit. If the on-site UPT is positive, a serum pregnancy test will be done. For post-menopausal women <60 years or of age, a serum FSH will be done at the screening visit only.

d. Sites will use a centralized computer-based system to obtain the randomization bottle(s) assigned to each subject.

- Subjects with baseline CSBMs from 0 to 0.9 will be randomized to begin treatment with ENT-01 150 mg or 6 tablets of placebo.
- Subjects with baseline CSBMs from 1.0 to 3.0 will be randomized to begin treatment with ENT-01 75 mg or 3 tablets of placebo.
- Subjects will self-administer study medication at home. The dose will be taken upon awakening, on an empty stomach with 8 oz. of water.
- Subjects will be advised to stay at home for 4 to 6 hours after taking the first dose of medication in case there is a need to evacuate urgently. After the first dose, subjects will know if and when to leave the house.

- e. A subset of 20 subjects from this study population will participate in an L-Dopa PK Study, as follows:
 - Visits 2 and 6: Blood draws for L-dopa levels (PK) will be drawn at Time zero.
 - The first daily dose of L-Dopa will be administered on site after the first blood draw. There will be another blood draw at 20, 40, and 60 minutes post- L-Dopa dose
 - Visits 3, 4, and 5: Immediately upon arrival at the study site, the subject will take study medication (ENT-01 or placebo) on an empty stomach. Blood will be drawn at Time zero. 30 to 60 minutes after taking ENT-01 or placebo, the subject will take their first daily dose of L-Dopa. Blood will be drawn again 20, 40, and 60 minutes post-L-Dopa dose. The subject may have food 60 minutes after taking ENT-01.
- f. Rescue medications will be dispensed as needed and instructions given concerning laxatives and other medications to treat constipation.
- g. Subjects will be educated concerning use of the electronic diary to report stools immediately after a bowel movement
- h. The first 3 parts of the MDS-UPDRS should be administered while the subject is in an ON state, approximately one hour after taking L-Dopa (if applicable). In some cases, patients will reach the “on” state earlier or later than at 60 minutes. In those cases, MDS-UPDRS should be performed when the patient is “on”.
- i. Those subjects who have a SAPS-PD score >0 on Visits 1 and 2 will have the SAPS-PD and hallucination/delusion questionnaire at all subsequent visits.
 - If only Visit 1 or Visit 2 has a score >0 , then SAPS-PD will not be repeated in subsequent visits.
- j. The stool sample should be collected during the EoT visit if the subject does not wish to return for the Washout Visit.

2.5. Study Periods

The study consists of the following periods:

1. **Screening Period:** This period lasts from Visit 1 to the day before Visit 2 (Day of randomization)
2. **Treatment Period:** This period lasts from Visit 2 (day of randomization) to the day before Visit 4 (start of single blind placebo period) and is divided into two sub-periods
 - 2.1. **Dose Escalation Period:** This period starts at Visit 2 and ends when the subject is on a Fixed Dose of study medication.
 - 2.2. **Fixed Dose Period:** This period starts when the subject is on a Fixed Dose of study medication and lasts until Visit 4. The fixed dose period is only defined if the subject was in the treatment period for at least seven days after the date of randomization. In the event that a subject is on the same dose until the start of the single blind placebo period or until withdrawal from treatment after being in the treatment period for at least seven days after randomization, then the fixed dose period will be the entire treatment period and the dose escalation period will not be defined. If the subject was not on their fixed dose for at least seven days, then the fixed dose period will extend to the subject's last seven days of treatment (including fixed dose) in order to derived rate variables during the fixed dose period, as described in Section 4.7. Missing diary entries in the middle of treatments of the same dose are not considered when determining the start of the fixed dose period.
3. **Single Blind Placebo Withdrawal Period:** This period starts at Visit 4 and ends at Visit 5. Weekly rate derivations during the single blind placebo withdrawal period will not include assessments on the Visit 4 date.
4. **Wash Out Period:** This period starts at Visit 5 and ends at Visit 6.

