9.2.4 Efficacy Analyses

9.2.4.1 Primary Efficacy Endpoint Analyses

The primary efficacy endpoint is the change from baseline in weekly CSBM rate during the Fixed Dose period. The primary analysis will be based on the Efficacy Evaluable Population. The primary efficacy analysis will be performed via an analysis of covariance (ANCOVA) model with change from baseline in weekly CSBM rate as the dependent variable, treatment (active or placebo) as a factor, and a subject's baseline weekly CSBM rate as a covariate. The comparison of active versus placebo treatment group will be tested at the two-sided 0.05 significance level. Summary statistics will also be presented.

As a supplemental analysis, the treatment effect for the primary efficacy endpoint will be summarized by the weekly CSBM rate subgroups (0-0.9, 1.0 – 3.0). The primary efficacy analysis will also be performed on the mITT and Fixed Dose Populations.

As an additional supplemental analysis, the change from baseline in weekly CSBM rate using the subject's last 2 weeks of the Treatment Period will be analyzed using the ANCOVA model described for the primary endpoint using the mITT population.

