2.6. Efficacy, Pharmacokinetic, Safety and Tolerability Endpoints

2.6.1 Efficacy Endpoints

Primary Efficacy Endpoint

The primary efficacy endpoint is the change from baseline in the weekly CSBM rate during the Fixed Dose period.

Baseline is defined as the weekly CSBM rate during the 2-week screening period. If a subject has more than two weeks of entries during the screening period, consecutive missing entries during the screening period will be excluded from baseline calculations, and the last fourteen days with entries during the screening period will be used to derive baseline weekly rates.

Subjects with fewer than 11 days of diary data during screening would be excluded from the study. The primary efficacy endpoint will be obtained as the weekly CSBM rate during the Fixed Dose period with exceptions as noted in section 4.7. The frequency of CSBMs will be

determined via a web-based electronic diary where the passage of a bowel movement or absence thereof will be recorded daily throughout the study by the subject.

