3. SUBJECT POPULATIONS

3.1. Population Definitions

The following subject populations will be evaluated and used for presentation and analysis of the data:

- **Safety Population:** The Safety Population will consist of all subjects who receive at least one dose of study medication during the study. Subjects will be analyzed based on the treatment that they actually received. All safety analyses will be based on this population.
- **Modified ITT Population:** The modified Intent-to-Treat (mITT) Population will include subjects who are randomized and have the stool diary assessments both at baseline and at least one post baseline time-point. Subjects who are found later to have inclusion/exclusion violations will be excluded from the mITT population.
- **Fixed Dose Population:** The Fixed Dose Population will include all subjects who are in mITT Population who enter the Fixed Dose period of the study and are in the treatment period for at least seven days, not including the date of randomization.
- **Efficacy Evaluable Population:** The Efficacy Evaluable Population will include subjects who are in the Fixed Dose Population, complete the Fixed Dose period, are compliant with study medication in the Fixed Dose period, and have no major protocol deviations.
- **Pharmacokinetics Population:** Pharmacokinetics Population will include subjects with a least one L-Dopa PK result.

The precise reasons for excluding subjects from the Efficacy Evaluable Population will be fully defined and documented prior to the unblinded interim analysis.

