4.6. Efficacy Analyses

Efficacy analyses to evaluate the treatment effect will be conducted using the Fixed Dose population as the primary population. The analyses will also be performed using the mITT and Efficacy Evaluable populations. Summary statistics will also be presented.

The comparison of active versus placebo treatment will be tested at the two-sided 0.05 significance level.

The date of randomization will not be included for either baseline or post-baseline weekly efficacy endpoints (i.e., rates or mean values). Similarly, the date of the single-blind period visit will also not be used in derivation of weekly efficacy endpoints (rates or mean values). Also, the visit 5 Date (ie, the date the patient begins the Washout period) will be included in the single-blind period (i.e., the single-blind period lasts from the day after Visit 4 up to and including Visit 5).

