4.6.3 Analysis of the Primary Efficacy Endpoint

The primary efficacy endpoint is the change from baseline in weekly CSBM rate during the Fixed Dose period. The primary analysis will be based on the Fixed Dose Population. The primary efficacy analysis will be performed via an analysis of covariance (ANCOVA) model with change from baseline in weekly CSBM rate as the dependent variable, treatment (ENT-01 or placebo) as the independent variable, and baseline weekly CSBM rate as a covariate.

As a supplemental analysis, the treatment effect for the primary efficacy endpoint will be summarized by the weekly CSBM rate subgroups (0 – 0.9, 1.0 – 3.0). The analysis will be performed for both Efficacy Evaluable population and Fixed Dose population.

The study will be considered a success if the p-value for the comparison of treatment groups from the ANCOVA model using the Fixed Dose population is significant (p<0.05).

Change from baseline in weekly CSBM rate will also be summarized by the specific fixed dose for patients. These summaries will be descriptive in nature only and no inferential statistics will be performed.

A linear trend test for weekly CSBM rate within each treatment group across baseline, fixed dose, and single blind periods will be conducted by using mixed model repeated measures (MMRM) methods, where the Baseline, Fixed Dose, and Single Blind periods are assigned values of 0,1, and 2 respectively for modeling purposes. Baseline CSBM rate (0-0.9/1.0-3.0) is included as a factor, with subject intercept and slope as random effects in the mixed model. The trend test will also be conducted across all subjects, including both Placebo and ENT-01 treatment groups in the model as a factor (fixed effect).

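### Under the SAP a subject treated for fewer than 7 days has no primary-endpoint value, so the mITT run of the primary ANCOVA cannot show the effect of first-week dropout

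*SAP*

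**What the plan says.** SAP 2.6.1 fixes the endpoint: "The primary efficacy endpoint is the change from baseline in the weekly CSBM rate during the Fixed Dose period". SAP 2.5 then limits who can have one: "The fixed dose period is only defined if the subject was in the treatment period for at least seven days after the date of randomization".

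SAP 3.1 defines two of the populations that matter here:

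- mITT: randomized subjects who "have the stool diary assessments both at baseline and at least one post baseline time-point", less those later found to violate the entry criteria.
- Fixed Dose: mITT subjects meeting a further condition: "enter the Fixed Dose period of the study and are in the treatment period for at least seven days, not including the date of randomization".

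SAP 4.6.3 names the primary set: "The primary analysis will be based on the Fixed Dose Population". It judges success on that set alone. SAP 4.6 adds: "The analyses will also be performed using the mITT and Efficacy Evaluable populations". It gives no separate mITT endpoint, window or imputation.

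The protocol (9.2.4.1) also wants the mITT run: "The primary efficacy analysis will also be performed on the mITT and Fixed Dose Populations". In the same section it plans one more ANCOVA, on mITT, using the CSBM rate over each subject's last 2 weeks of treatment. The SAP's efficacy sections do not contain that analysis, yet SAP section 5 declares no departures from the protocol's analyses. The protocol's own Fixed Dose Population (9.0) carries no 7-day condition.

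**The concern.** The point of a wider population is to bring back subjects whom the primary set leaves out. On paper mITT does this, since one diary assessment after baseline is enough. In practice the model needs a dependent variable, and a subject with 1 to 6 treatment days has none.

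Remaining on treatment for a week is a post-randomization event that could depend on the arm. Phase 2a (protocol 2.2) reported nausea in 21 of 44 subjects and diarrhea in 18 of 44, although not specifically in the first week. Protocol 4.2 warns subjects of urgent evacuation after the first dose. If tolerability removes more ENT-01 than placebo subjects early, the comparison is between those who tolerated the tablets and nearly everyone on placebo. The mITT run would be the natural place to see this, and as written it cannot.

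**Working it through.** **Who gets a value.** Taking SAP 2.5, 2.6.1, 3.1 and 4.6.1 together, and assuming the diary condition for mITT is met:

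| Treatment days | Fixed dose reached? | In mITT | Fixed Dose rate exists | In Fixed Dose Population |
|---|---|---|---|---|
| 1–6 | yes or no | yes | no | no |
| 7 or more | yes | yes | yes (a short period is extended back to 7 days) | yes |
| 7 or more | never | yes | strict reading of 2.5: no; looser reading of 4.6.1: yes | no |

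Every treatment length from 1 to 25 days was enumerated, with a fixed dose reached on any day or never. On the strict reading, no pattern separates the mITT subjects with an endpoint from the Fixed Dose Population. On the looser reading, the whole 7-day window may come from escalation days; the only patterns that differ are 7 to 25 days with no fixed dose, that is, subjects still escalating. On neither reading does anyone with under 7 days obtain a value.

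**Whether another rule rescues them.** Two rules in SAP 4.6.1 might seem to.

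- Borrowing escalation days to make up 7 cannot work with fewer than 7 treatment days.
- Counting a missing diary day as zero CSBMs operates within a period. It does not create a period that 2.5 leaves undefined.

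SAP 2.5 and 2.6.1 refer to section 4.7 for the derivation and its exceptions, but 4.7 is the pharmacokinetic analysis. The derivation is in 4.6.1.

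**A planning figure, as a check on inputs.** SAP 4.1 states 90% power for part 1: 64 evaluable subjects at 3:1 (48 and 16), difference 2.4 − 0.5 = 1.9, SD 2.0, two-sided 0.05. The noncentrality is 1.9 / (2.0 × √(1/48 + 1/16)) = 3.29 on 62 df, which gives 90.0%. The figure reproduces; the present point does not rest on it.

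**Possible size.** Protocol 9.2.5 plans mean changes of 3.55 and 1.28, a difference of 2.27. Let a and b be the first-week losses on ENT-01 and placebo, give leavers zero change and stayers the planned means:

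difference = 3.55 × (1 − a) − 1.28 × (1 − b)

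| a, b (assumed) | Calculation | Difference | Against 2.27 |
|---|---|---|---|
| 5%, 0% | 3.3725 − 1.2800 | 2.09 | −8% |
| 10%, 3% | 3.1950 − 1.2416 | 1.95 | −14% |
| 15%, 5% | 3.0175 − 1.2160 | 1.80 | −21% |

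The mITT run as written would show none of these reductions.

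**Why a rate from the available days is not the answer.** SAP 4.6.1 multiplies CSBMs per day by 7. Under CSBM Definition 1, a stool scored 6 or 7 counts as complete even if the subject reports more to pass. Four such stools a day for 2 days, with no rescue medication, give 7 × 8 / 2 = 28 per week. With an assumed baseline of 1, the change is 27. One such subject among 40 moves the ENT-01 mean from 3.55 to (39 × 3.55 + 27) / 40 = 4.14. Early intolerance would be scored as efficacy. Over a fixed 14 days with no further CSBMs, the same subject has 7 × 8 / 14 = 4 per week.

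**The case against.** - **Early leavers are not absent from the SAP.** A reader might infer that they appear in no analysis at all. The documents do not support that. Dosed subjects are in the safety and tolerability analyses (4.8), and early leavers are in the disposition (4.4) and demographic (4.5) summaries. They may also enter the exploratory washout ANCOVA (4.6.5), because protocol section 4 asks those who stop drug to complete the Wash-Out. This stands: the gap concerns the primary endpoint only.
- **The two sets need not be identical.** A reader might also infer that the mITT and Fixed Dose results must coincide. That follows only on the strict reading of 2.5. SAP 3.1 requires both entry into the Fixed Dose period and 7 days, so on the looser reading some subjects are in mITT alone. This stands too, but it brings back nobody with under 7 days.
- **The mITT run does not decide success.** SAP 4.6.3 uses the Fixed Dose Population, and no passage calls agreement between sets a proof of robustness. This stands and limits the severity.
- **The loss rates are assumed.** The 25% early termination in protocol section 4 concerns completing all visits, and the 64 of 72 evaluable in SAP 4.1 is not specific to the first week. The table above shows scale only.

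**Conclusion.** The point holds for the primary endpoint: early leavers are in no SAP analysis of it, and the mITT run cannot reveal what their exclusion does. This follows from the SAP's definitions and needs no assumption.

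The size is unknown. On assumed losses, with leavers at zero change, the planned difference falls by 8% to 21%. The direction also depends on who leaves: with no ENT-01 loss and 5% on placebo, the same formula gives 3.55 − 1.216 = 2.33, slightly above 2.27.

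The omission of the protocol's last-2-weeks mITT ANCOVA makes this worse. It is the protocol's one on-treatment CSBM analysis without the 7-day condition, and it was lost while section 5 reports no change. Because success rests on the Fixed Dose Population, this should be fixed, but it does not by itself invalidate the primary test.

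**What to change.** 1. In SAP 4.6.1 and 4.6.3, for the mITT analysis, set change from baseline to 0 for every mITT subject without a defined Fixed Dose rate. Require the number in the mITT ANCOVA to equal the mITT count.
2. Restore the protocol's last-2-weeks mITT ANCOVA, with a stated rule for short treatment that does not scale up 1 to 6 days alone. One option is a fixed 14-day denominator that uses diary days after stopping where collected and counts missing days as 0, as 4.6.1 already does. Correct section 5.
3. State whether a subject treated for 7 or more days who never reached a fixed dose belongs to the Fixed Dose Population and has a Fixed Dose rate. Correct the references to 4.7.
4. If a rate from all available days is wanted for subjects with under 7 days, keep it as a labelled sensitivity run only.

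The cost is SAP wording and one or two extra model runs, with no new data, settled before unblinding. The zero-change assumption is conservative for ENT-01 if leavers are mainly on active treatment, and not if they are mainly on placebo, so leaver counts should be shown by arm.
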